	NHS indemnity scheme will apply. It provides cover for the design, management, and conduct of the study.	23

22.	Dissemination of research findings	23
23.	References	23

2. Glossary

Dyspareunia – pain with penetrative sex.

FSD - Female Sexual Dysfunction

FSFI - Female Sexual Function Index

FSDS - Female Sexual Distress Scale

GPPD - genito-pelvic pain/penetration disorder. This diagnostic term recognises the frequent overlap between the conditions of vaginismus and vulvodynia

Vaginismus results from the involuntary spasm of the pelvic floor muscles which surround the vaginal wall.

Vulvodynia chronic vulvar pain of at least three months duration

Vestibulodynia – Often used to describe vulvar pain at the introitus, or entrance to the vagina

3. Signature page

Chief Investigator Agreement

The study as detailed within this research protocol will be conducted in accordance with the principles of Good Clinical Practice, the UK Policy Framework for Health and Social Care Research, and the Declaration of Helsinki and any other applicable regulations. I agree to take responsibility for the statistical analysis and oversight of this study.

Chief Investigator Name: [name]

Signature: [name]

Date: _____ 20/09/2022

4. Summary and synopsis

Short title	Feasibility of use of vibrators with vaginal dilators for vaginismus
Methodology	Feasibility study
Research sites	AKC, Barts Health NHS Trust, [name]
Objectives / aims	
Firstly, is vibration therapy (through the use of handheld vibrators on clitoral and vulval area) acceptable to women as part of medical management of vaginismus, alongside current medical management.
 
Does the use of external genital (clitoral/ vulval) vibrators help women to progress more easily with the use of vaginal dilators compared to women not using these? Is there any self-reported difference in experiences of pleasure or enjoyment around sexual experiences in the two groups of women? Are there any differences noted in reported ability to have penetrative sexual intercourse?

Number of participants	30
Inclusion and exclusion criteria	
Inclusion:
 
Female
 
>18 years old
 
Clinical diagnosis of Vaginismus (self-reported difficulties with penetration and genital exam consistent with a degree of vaginismus)
 
Willing to be enrolled in pilot study:

	
Exclusion:
 
Any vulval skin dermatoses excluding medical management of vaginismus
 
Transgender male / on testosterone therapy
 
Symptoms of genital herpes episode in preceding 3 months
 
Unable to speak/ understand English or needing an interpreter
 
Declines to be enrolled in research study
 
Pregnancy

Statistical methodology and analysis (if applicable)	n/a
Study duration	Up to 48 months

5. Introduction

VITA DIVA- Vibration Therapy And Dilators for Vaginismus

Vaginismus results from the involuntary spasm of the pelvic floor muscles which surround the vaginal wall. This can make sexual intercourse uncomfortable, painful, or impossible, with resultant impacts on a woman's sexual pleasure and ability to conceive. There is often overlap with vulvodynia (also termed vestibulodynia), chronic vulvar pain of at least three months duration. Various clinical definitions have been proposed for vulvodynia or vestibulitis.

Successful treatment for both vulvodynia and vaginismus relies often on both medical and psychosocial interventions alongside self-help and practice. Current medical therapy for vaginismus often consists of the use of topical local anaesthetic gel, sometimes in addition to oral medications such as low dose Tricyclic Antidepressants together with recommendation of progressive vaginal dilator therapy (often termed systemic desensitisation) and physiotherapy. The fact there is not a clearly culpable etiology (and indeed causes are likely to be multifactorial) means that there is no 'gold standard' treatment for vaginismus and vulvodynia (Zolnoun, 2008). A multi-modal approach is recommended.

Anecdotally, some women find that clitoral stimulation can sometimes have a positive impact on the ability to progress with vaginal dilator treatment and general enjoyment of sexual intimacy, but this has not yet been evaluated in a research setting.

Background

Various clinical definitions exist for vaginismus and vulvodynia, which have been recognised as a syndrome by the American Medical Association in the DSM-5 as genito-pelvic pain/penetration disorder (GPPD). This diagnostic term recognises the frequent overlap between the conditions of vaginismus and vulvodynia (AMA, 2013). Diagnosis per the DSM-5 criteria requires the presence of one of the following: persistent or recurrent difficulties with vaginal penetration during intercourse; marked vulvovaginal or pelvic pain during penetrative intercourse or attempts; fear or anxiety about vulvovaginal or pelvic pain in anticipation of, during, or as a result of vaginal penetration; or marked tensing or tightening of the pelvic floor muscles during attempted vaginal penetration. Additional criteria are presence of symptoms for at least six months, significant distress, and not explained by a diagnosis of non-sexual disturbance, causing relationship problems and not attributed to the effects of any substance or any other medical condition.

In review of literature, searched for the terms vulvodynia, vestibulodynia, female genital pain, sexual disorders, and vibration, vibrator or clitoral or genital stimulation. Of the 85 results, 9 were relevant and in English. Of these, one related to the use of vaginal dilators, 5 related to genital vibratory stimulation devices, 3 related to genital stimulation and perception of pain. No studies assessing the acceptability of clitoral vibrators specifically in self-treatment of patients with vaginismus were found.

Genital stimulation/ sensation and pain perceptions

Calens et al carried out a web-based questionnaire of sexually active women n=256, median age 22 range 18-49. Questions included the Female Sexual Function Index (FSFI) and the Female Sexual Distress Scale (FSDS). Women reported the clitoris to be more sensitive than the vagina in terms of pleasurable responses, but not painful response. Women with Female Sexual Dysfunction reported impaired self-perceived genital sensation, less sexual pleasure and orgasm, and more association of orgasm with discomfort in the genital area than women without FSD. They conclude that “enhancing the pleasurableness of genital sensations, especially during partnered sex, could decrease the likelihood of experiencing pain and concomitant FSD” (Calens, 2016).

Paterson et al found that women who masturbated to orgasm in private found that this appeared to maintain pleasurable genital sensitivity, but increase in pain sensitivity with higher vulvar pain sensitivity when orgasm occurs. Enhancing stimulation pleasurableness, psychological sexual arousal can mitigate normative increases in pain sensitivity during sex(Paterson, 2013).

Whipple et al investigated the effectiveness of genital self-stimulation in elevating pain thresholds. This was a study of only 10 women who applied pleasurable sensations to the anterior vaginal wall, the posterior vaginal wall, and the clitoris. Increases in pain thresholds but not tactile thresholds were noted in this group compared to distraction control (Whipple, 1988).

Use of devices in self-directed therapy for vaginismus and vulvodynia:

One study assessed the acceptability of vulvar vibration therapy as a treatment for vulvodynia. 69 patients enrolled of whom 49 were eligible for analysis. Vulvar pain and dyspareunia were the primary complaints, and median duration of these was two years and three years respectively (Zolnoun, 2008). Although this may be a somewhat different population; (the primary presenting complaint was vulvodynia or dyspareunia, as opposed to vaginismus, and only two of the 49 had ever used vaginal dilators). Furthermore, it was acknowledged in the study that the generalisability of results was limited as the study population was primarily white, married, well-educated and from a single geographical location. 83% of those surveyed who had used vulvar vibration therapy for at least two weeks had found it an acceptable and 73% found it a convenient treatment. In this study, Zolnoun et al. proposed that VVT therapeutic rationale was based on the anti-nociceptive properties of vibration and on the favourable response of vulvodynia to physical therapy.

Genital vibration devices were found to result in improvements in sexual function, satisfaction, sexually related distress and genital sensation in women with arousal and orgasm disorders in one study enrolling 70 women, 37 of whom were followed up after a period of 3 months (Guess, 2017). This was a single-arm study enrolling women with arousal and/or orgasm disorders, so again a slightly different study population to the proposed study. Mean age was 35.5, and 66% had never or seldom used genital vibratory device. The Female Sexual Function Index (FSFI) and the Female Sexual Distress Scale (FSDS) were carried out at baseline and follow up which was at 3 months.

Herbenick et al acknowledged that vibrators are frequently recommended by clinicians for female sexual dysfunction, although there is little awareness of the correlation of this to sexual function. 2, 056 women participated in the internet based

survey (54% of the 3,800 nationally representative sample who were invited). This assessed the prevalence of vibrator use, and the relationship between vibrator use and psychological well-being. The Female Sexual Function Index was used. Prevalence of vibrator use was 52.5%, and use was significantly correlated ($P<0.001$) with having performed genital self-examination in the past month. Vibrator use was associated with more positive sexual function (including higher levels of desire and arousal and lower levels of pain). It was rarely associated with side effects (Herbenick, 2009).

Rubin et al and Billips et al published clinical guides for role of mechanical devices in treating female sexual dysfunction. These acknowledge the paucity of clinical evidence of effectiveness but also highlight the fact that these are generally safe and without significant adverse effect. (Rubin 2019; Billips 2002)

Proposed study

The acceptability of vulvar vibration therapy has been evaluated in women with vulvodynia, and found to be acceptable, however has not been assessed in women with a primary complaint of vaginismus.

This proposed study looks at the feasibility and acceptability of using clitoral vibration therapy, alongside current therapy, for women with vaginismus. It is likely that many, if not most, of these women will also have an element of vulvodynia. We propose that the use of external clitoral or vulval vibration therapy is likely to be acceptable in most women with vaginismus, based on acceptability of vulvar vibration therapy in women with vulvodynia. We propose based on the evidence above that vibrator therapy may help women with female sexual dysfunction to use vaginal dilators, based on study showing improvements with sexual distress and satisfaction.

Enrollment

This is a nonrandomized controlled trial, with the initial cluster of patients receiving standard therapy, and the second cluster receiving standard therapy plus vibrator. We aim to recruit an initial 15 participants who will receive standard therapy, and another 15 who will receive an external vibrator.

We expect this to take place over approximately 24-48 months. Enrollment of patients will be from a joint psychosexual clinic led by a medical doctor and a clinical psychologist. Female patients are referred to this clinic by General Practitioners, from within the Sexual Health service, or via Gynaecologists, frequently with complaint of difficulty or pain with penetrative sex. Inclusion and exclusion criteria have already been outlined.

Trial information will be given at the initial appointment. If the patient wishes to enrol, then an initial baseline questionnaire will be given, and a follow up questionnaire will be filled out by phone contact at 6-24 months afterward the initial consultation at the patients consent.

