6.1 Primary objective

Is vibration therapy (through the use of handheld vibrators on clitoral and vulval area) acceptable to women as part of medical management of vaginismus and vaginismus/vulvodynia, alongside current medical management.

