6.3 Primary endpoint

Baseline and follow up questionnaires will be used – to assess acceptability and perceived acceptability of control therapy and intervention.

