The follow up questionnaires will be filled out by phone contact 6-24 months after the initial consultation at the patients consent if they agree to remain enrolled in the trial for both group 1 and group 2. This will take approximately 30 mins and will be arranged at a time convenient for the patient. This interview will be carried out by a doctor. Answers will be recorded directly onto the follow up questionnaire proforma.

4 point Likert scale 1 (Strongly disagree) to 4 (Strongly agree)

9. Study procedures

- Informed consent – verbal and written will be given, patients will be offered opportunity to enrol on the day (for convenience) or to return at another point to enrol.
- Screening and recruitment – as outlined previously recruitment will be directly from clinic
- Randomization – this is a non-randomized controlled trial, as trial participants need to be identified as time goes on, and a certain number of control and intervention participants are needed. The initial 10-15 recruited will receive standard treatment, and then the next 15 will receive intervention.

Study interventions

Study intervention	Contact (Visit) 1	Contact 2		
Medical history	X			
Consent	X			
Baseline Questionnaires (FSDS, FSFI, custom questionnaire)	X			
Phone Interview (FSDS, FSFI, custom questionnaire)		X		

Vaginal dilators will be provided to both groups (if available) and external genital vibrators to the second (intervention) group.

- Concomitant medications – per standard treatment, patients with vulvodynia may be prescribed topical lidocaine gel and may also receive nortriptyline if there is unprovoked vulvodynia present.
- Criteria for discontinuation – if patients withdraw consent for being enrolled in the study then follow up will discontinue.
- Procedure for collecting data, including Case Report Forms (CRFs) and storage: CRFs will be filled out electronically, and stored in a password protected file. The research data will be archived for 25 years according to Queen Mary University of London/ Barts Health NHS Trust policy, JRMP SOP 20.

- Follow up will be via phone interview. Patients enrolled will receive a contact email address in case of queries in the meantime during research period.
- End of study duration will be at follow up questionnaire (at 6-24 months post initial appointment and questionnaire)

10. Assessment and management of risk

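### Acceptability is measured only in women who enrol and stay enrolled, with no count of women offered the study or declining it, so uptake, half of the feasibility question, goes unmeasured

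*Protocol*

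**What the plan says.** The primary objective (Protocol 6.1) is whether vibration therapy is "acceptable to women as part of medical management of vaginismus and vaginismus/vulvodynia, alongside current medical management". Section 5 (Proposed study) says "This proposed study looks at the feasibility and acceptability of using clitoral vibration therapy" and expects it to be acceptable to most women with the condition.

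Section 6.3 gives the only measure: "Baseline and follow up questionnaires will be used – to assess acceptability and perceived acceptability of control therapy and intervention". Two other places settle who answers:

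- Baseline, section 5 (Enrollment): "If the patient wishes to enrol, then an initial baseline questionnaire will be given".
- Follow-up, section 8 (Both groups): women are telephoned "if they agree to remain enrolled in the trial for both group 1 and group 2".

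The synopsis lists "Willing to be enrolled in pilot study" as an inclusion criterion and "Declines to be enrolled in research study" as an exclusion. Section 7.2 likewise excludes women who do not consent.

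Allocation follows recruitment order (section 9, Randomization): "The initial 10-15 recruited will receive standard treatment, and then the next 15 will receive intervention".

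Sections 14.1 and 14.2 name the data to be captured: medical records and the two questionnaires.

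**The concern.** The objective and the hypothesis concern women with vaginismus who attend the clinic. The measurement covers only those who agreed to join a study of vibrators. A woman who finds the idea of a vibrator unacceptable may decline the study for that reason, and the protocol describes nothing that would record that she was asked.

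The protocol itself makes such refusals plausible. Sections 10 and 12 say that patients can find these discussions embarrassing, and section 12 expects that explaining how to use a clitoral vibrator will take extra clinic time.

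The results are meant to guide what clinicians recommend (section 5.3) and to support recommending vibration therapy (section 22). A clinician making that recommendation needs to know two things: how many women take up the offer, and how those who took it up judged it. The planned data address only the second. For a study described throughout as one of feasibility, section 6 has no objective or endpoint on uptake.

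**Working it through.** **1. Is there a figure of the plan's own to reproduce?** Only the total of 30 (section 11.1), which agrees with 15 + 15 in section 5 (Enrollment). It is a recruitment expectation. No precision target, acceptability threshold or refusal rate is stated, so the rest is a comparison of passages plus an illustration.

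**2. Path of a woman through the study.**

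| Stage | Source | Recorded? |
|---|---|---|
| Identified as suitable by the clinician | section 7 | no count described |
| Offered the study, verbally and by leaflet | section 7 | no count described |
| Declines | synopsis, section 7.2 | no count or reason described |
| Enrols, baseline questionnaires | sections 5 and 8 | yes |
| Follow-up questionnaires by telephone | section 8 | yes, if still enrolled |

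Women who enrol and later withdraw can still be counted, because the number enrolled is known. Women who decline at the start cannot.

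**3. Illustration of what the data cannot separate.** Define:

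- Uptake: U = enrolled / eligible women offered.
- Acceptability among enrolled women who answer: A = rating acceptable / enrolled.

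Assume that 15 women enrol in the vibrator group, 12 rate it acceptable, and *r* further eligible women decline because of the vibrator. The 12 and the values of *r* are assumptions; the protocol gives neither. The last column is a limiting case that counts every such decliner as not finding the vibrator acceptable: 12/(15 + *r*) = U × A. Brackets show exact (Clopper–Pearson) 95% intervals.

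| *r* | Offered | U | A | 12/(15 + *r*) |
|---|---|---|---|---|
| 0 | 15 | 15/15 = 100% | 12/15 = 80% | 80% (52–96) |
| 5 | 20 | 15/20 = 75% | 80% | 60% (36–81) |
| 10 | 25 | 15/25 = 60% | 80% | 48% (28–69) |
| 15 | 30 | 15/30 = 50% | 80% | 40% (23–59) |

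Column A is all that the planned data can give, and it is the same in every row.

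**4. Does the cited evidence fill the gap?** The 83% from the vulvodynia study (sections 5 and 5.4) applies to women who had used the therapy for at least two weeks. It too is conditional on having taken up the therapy, so it says nothing about uptake.

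**The case against.** - **Consent is always required.** This stands. A reader might infer from the exclusion criterion that the eligibility rule itself answers the primary question. The documents do not support that: no study can collect questionnaires from women who refuse, the criterion concerns declining the research rather than the vibrator, and enrolled women can still report that they find the vibrator unacceptable.
- **Women decline for other reasons.** True: the telephone interview, time or privacy, for example. That is why reasons are worth recording, and why uptake should be split by period.
- **Group 2 bias.** A reader might infer that Group 2 is more willing to use a vibrator than Group 1, which would bias the secondary comparison. That would require women to know their group before consenting. The protocol does not say so; section 8 describes trial information under both groups together, and section 7 describes a single leaflet. If both groups receive the same information, the differential selection may largely disappear.
- **Refusers replaced by accepters.** A reader might also infer that recruitment runs until each group is full. The protocol does not state this. Group sizes appear as 10–15 (section 8), 15 (section 5) and 15–20 (section 11.1), so slow recruitment might simply leave a smaller group.
- **Acceptability after use is a legitimate target.** It is, and the cited vulvodynia study used it. Willingness to try and experience of use are different constructs, so 12/20 should not be reported as an acceptability rate. The endpoint also covers perceived acceptability, so baseline items may capture views before use, but still only among enrolled women.
- **A screening log or analysis plan may cover this.** A site log may exist, but the protocol does not describe one. An analysis plan cannot recover refusals and reasons that were never recorded.

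**Conclusion.** The point holds in a limited form. As written, the study can describe acceptability among women who agreed to take part and stayed in. It cannot say how that relates to acceptability among women with vaginismus who are offered a vibrator, although objective 6.1 and the hypothesis in section 5 are worded for that wider group. The defect is the missing record of women offered and declining, together with the absence of an uptake measure in section 6.

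The size is unknown. If few women decline because of the vibrator, the gap is small. If as many decline as enrol, uptake is 50% while the reported result is unchanged. The figures shown are illustrations under assumed counts and are not evidence of how large the gap is. Any difference in willingness between Group 1 and Group 2 remains conditional on what women are told before consent. This is a worthwhile, cheap improvement and does not invalidate the design.

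**What to change.** 1. Add to section 6.3 a descriptive uptake measure: women enrolled divided by eligible women offered the study, reported separately for the standard-treatment and vibrator recruitment periods.
2. Add to section 14.1 an anonymous clinic tally, by period, of women eligible, offered and declining, with the reason if volunteered, including not wanting a vibrator.
3. Report uptake beside the questionnaire result and do not merge the two into one percentage.
4. State in 6.1 or 6.3 that the questionnaire result applies to women who agreed to take part.
5. State in section 7 or 9 whether women know their group before consenting, so that the two uptake figures can be interpreted.

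Eligibility, treatment and sample size do not change. The cost is a line of tally for each eligible patient, kept by the clinicians who already identify participants. Some women will give no reason, so the breakdown of reasons will be incomplete.

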5.1 Preclinical data

Preclinical trials are not applicable in this study.

Vibrators we propose to use in this study are not medical devices and are made from FDA-approved medical grade silicone.

5.2 Clinical data

A full description of available and relevant clinical data is documented in the review of literature in section 5.0.

Clinical data which will be gathered at baseline in order to compare two groups: Age, Parity, previous vaginal delivery, postmenopausal/premenopausal, gynaecological surgery, sexual orientation, patient self-described ethnicity, gender

